2.6 Analysis of the key secondary objective

[figure not shown]
There is no key secondary objective.

2.7 Analysis of secondary efficacy objective(s)

2.7.1 Secondary endpoints

The following endpoints are defined as secondary:

- change from baseline to month 36 in quadrant RNTFT, i.e. nasal-superior, nasal-inferior, temporal-superior, and temporal-superior RNFLT

2.7.2 Statistical hypothesis, model, and method of analysis

No hypothesis is to be tested. P-values are displayed as descriptive measures.

Analysis is similar to the primary endpoint. All analyses are done with the FAS only.

Correlations in the change from baseline to month 12, month 24 and month 36 are presented by the Pearson correlation coefficient or Spearman Rank correlation coefficient, depending on distribution of data. Normality was graphically investigated..

Correlations are displayed graphically by scatter plots. Here, only changes from baseline to last value until Month 36 are displayed.

2.7.3 Handling of missing values/censoring/discontinuations

Missing values are replaced by the last available value. According to the definition of FAS (at least one post-baseline value of the primary parameter is required) all patients have a value after baseline.

In contrast to the primary parameter no sensitivity analysis without replacing the missing data is performed.

2.8 Safety analyses

All safety analyses were presented for the SAF population.

2.8.1 Adverse events (AEs)

Adverse events which started before BL/M0 were listed only. Analyses were performed on AEs which started at/after BL/M0.

The incidence of adverse events is displayed with n, percentage and 95% confidence interval for the SAF. Here, different types of AEs are presented:

- (1) Any AE
- (2) AE with suspected relationship to fingolimod
- (3) AE leading to study drug dosage adjustment/temporary interruption
- (4) AE leading to permanent study drug discontinuation
- (5) Serious adverse event
- (6) Non-Serious AE
- (7) Death

For AEs of type (1) to (6) a two-level frequency table for MedDRA system organ classes (SOC) and Preferred Terms (PT) within SOC are presented. Here, a patient with multiple occurrences is counted only once on the respective class.

The maximum severity of (several) AEs occurring in a patient ist displayed for PTs within SOC, SOC and overall.

For AEs of type (7), (5), and (3) separate listings are generated.

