8.1 Adverse Events (AEs)/Serious Adverse Events (SAEs)

An adverse event is the appearance or worsening of any undesirable sign, symptom, or medical condition occurring after first drug intake even if the event is not considered to be related to drug therapy. Medical conditions/diseases present before obtaining informed consent are only considered adverse events if they worsen after starting trial. Abnormal laboratory values or test results constitute adverse events only if they induce clinical signs or symptoms, are considered clinically significant, require medication discontinuation or require therapy.

The occurrence of adverse events should be sought by non-directive questioning of the patient at each visit during the trial. Adverse events also may be detected when they are volunteered by the patient during or between visits or through physical examination, laboratory test, or

other assessments. All adverse events must be recorded on the Adverse Events CRF with the following information:

1. its relationship to Fingolimod (suspected/not suspected)
2. its duration (start and end dates or if continuing at final exam)
3. whether it constitutes a serious adverse event (SAE)

An SAE is defined as an event which:

- is fatal or life-threatening
- results in persistent or significant disability/incapacity
- constitutes a congenital anomaly/birth defect
- requires inpatient hospitalization or prolongation of existing hospitalization, unless hospitalization is for:
 - routine treatment or monitoring of the studied indication, not associated with any deterioration in condition (e.g. hospitalization for relapse treatment)
 - elective or pre-planned treatment for a pre-existing condition that is unrelated to the indication under study and has not worsened since the start of study drug
 - treatment on an emergency outpatient basis for an event not fulfilling any of the definitions of a SAE given above and not resulting in hospital admission
 - social reasons and respite care in the absence of any deterioration in the patient's general condition
- is medically significant, i.e., defined as an event that jeopardizes the patient or may require medical or surgical intervention to prevent one of the outcomes listed above

Unlike routine safety assessments, SAEs are monitored continuously and have special reporting requirements; see Section 8.2.

Information about adverse reactions observed in relation to fingolimod can be found in the local product labeling.

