All adverse events should be treated appropriately. Treatment may include one or more of the following: no action taken (i.e., further observation only); medication temporarily interrupted; medication permanently discontinued due to this adverse event; concomitant medication given; non-drug therapy given; patient hospitalized/patient's hospitalization prolonged. The action taken to treat the adverse event should be recorded on the Adverse Event CRF.

Once an adverse event is detected, it should be followed until its resolution or until it is judged to be permanent, and assessment should be made at each visit (or more frequently, if necessary) of any changes in severity, the suspected relationship to the medication, the interventions required to treat it, and the outcome.

Information about side effects already known about the investigational drug can be found in the Investigator's Brochure (IB) or will be communicated between IB updates in the form of SUSAR reports for the investigator and if applicable in the form of Investigator Notifications. This information will be included in the patient informed consent and should be discussed with the patient during the study as needed.

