8.2 Serious adverse event reporting

To ensure patient safety, every SAE, regardless of suspected causality to a pharmaceutical product or procedure occurring in a study participant after the patient has provided informed consent and until 8 weeks after the patient has stopped study participation (defined as time last visit) must be reported to Novartis within 24 hours of learning of its occurrence.

Any SAEs experienced after this 8-week period should only be reported to Novartis if the investigator suspects a causal relationship to fingolimod.

Recurrent episodes, complications, or progression of the initial SAE must be reported as follow-up to the original episode, regardless of when the event occurs. This report must be submitted within 24 hours of the investigator receiving the follow-up information. An SAE that is considered completely unrelated to a previously reported one should be reported separately as a new event.

Information about all SAEs is collected and recorded on the Serious Adverse Event Report Form. The investigator must assess the relationship to fingolimod, complete the SAE Report Form in English, and send the completed, signed form by fax within 24 hours to the local Novartis Drug Safety & Epidemiology Department. The telephone and telefax number of the contact persons in the local department of Drug Safety & Epidemiology, are listed in the investigator folder provided to each site. The original copy of the SAE Report Form and the fax confirmation sheet must be kept with the case report form documentation at the study site.

Follow-up information is sent to the same person to whom the original SAE Report Form was sent, using a new SAE Report Form stating that this is a follow-up to the previously reported SAE and giving the date of the original report. The follow-up information should describe whether the event has resolved or continues, if and how it was treated, and whether the patient continued or withdrew from study participation.

If the SAE is not previously documented in the Investigator's Brochure (new occurrence) and is thought to be related to the Novartis drug, a Drug Safety & Epidemiology Department associate may urgently require further information from the investigator for Health Authority reporting. Novartis may need to issue an Investigator Notification (IN) to inform all investigators involved in any study with the same drug that this SAE has been reported.

Exception: Progression of multiple sclerosis / MS relapse

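### SAP 2.8.1 selects adverse events by start date alone, so an AE that began before Visit 2 but became serious, stopped fingolimod or was fatal after baseline is missing from the safety tables

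*SAP*

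**What the plan says.** SAP 2.8.1 sets the rule: "Adverse events which started before BL/M0 were listed only. Analyses were performed on AEs which started at/after BL/M0". The analyses that follow are incidences with 95% confidence intervals in the safety set for seven types: (1) any AE, (2) suspected relationship, (3) dose adjustment or temporary interruption, (4) permanent discontinuation of study drug, (5) serious, (6) non-serious, (7) death. SOC/PT tables for types (1) to (6) and a maximum-severity table are also planned. SAP 2.8.2 on deaths only refers back to 2.8.1.

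Protocol 8.1 defines the event more broadly: "An adverse event is the appearance or worsening of any undesirable sign, symptom, or medical condition occurring after first drug intake". For conditions that predate consent it adds: "Medical conditions/diseases present before obtaining informed consent are only considered adverse events if they worsen after starting trial". The timing it asks for is "its duration (start and end dates or if continuing at final exam"). Once an AE is detected, each visit is to include an assessment "of any changes in severity, the suspected relationship to the medication, the interventions required to treat it, and the outcome". Protocol 8.2 says of serious events: "Recurrent episodes, complications, or progression of the initial SAE must be reported as follow-up to the original episode, regardless of when the event occurs".

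Two other SAP outputs bear on the point. Section 2.4.1 shows fingolimod interruptions by incidence, reason, number and duration. Section 2.3.1 shows the number of, and reasons for, premature discontinuations from the study. Neither is filtered by AE onset.

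**The concern.** An AE has an onset, and it can have later consequences. The SAP places the whole AE on one side of baseline by its onset. If the onset is before Visit 2, a consequence during the 36 months of follow-up goes with it to a listing. The consequences that matter most for safety (seriousness, a drug stop, death) are on-study outcomes, and they belong to the stated safety and tolerability objective whenever the AE began.

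The situation can arise by design. Screening lasts up to 28 days, patients are already taking fingolimod during it, and Protocol 8.2 collects SAEs from consent. An AE can therefore start in screening and still be open at Visit 2. The omission runs one way: it can lower the reported incidences of AEs, interruptions, permanent stops, SAEs and deaths, and cannot raise them.

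**Working it through.** The plan states no AE rate or expected count, so there is no figure to reproduce. The check is textual, with arithmetic for scale only.

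**Step 1: which AEs can fall into the gap.**
- Condition present before consent that worsens after the trial starts: Protocol 8.1 makes the worsening itself the AE. If that happens after Visit 2, onset is after baseline and the AE is counted. Protocol 7.6.1 likewise sends significant findings present before the trial to the medical history page.
- AE that starts between consent and Visit 2 (screening, day -28 to day 0): onset is before BL/M0, so it is listed only, whatever follows.

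The clear window is therefore at most 28 days. The protocol's general wording dates AEs from first drug intake, which precedes consent here, so a few earlier onsets could also be recorded.

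**Step 2: which consequences are lost for such an AE.**

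| Event at or after BL/M0 | AE tables under SAP 2.8.1 | Other planned output |
|---|---|---|
| Temporary interruption | missing from type (3) | interruptions with reasons, SAP 2.4.1 |
| Permanent drug stop | missing from type (4) | SAP 2.3.1, only if the patient also leaves the study |
| Becomes serious | missing from type (5) | no other incidence |
| Death | missing from type (7) | SAP 2.8.2 points back; may appear as a reason in 2.3.1, without an incidence and CI |
| Worsening in severity | missing if kept under the old start date; counted if entered as a new AE | none |

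Stopping drug and leaving the study are not the same here. Protocol Appendix 7 wants patients who stop fingolimod for macular edema encouraged to stay. The separate AE listings named in SAP 2.8.1 cover types (7), (5) and (3), not (4).

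**Step 3: size per omitted patient.** Assume n = 100 in the safety set (the planned enrolment) and exact Clopper-Pearson intervals (the SAP names no method). One patient is 1/100 = 1.0 percentage point.
- 0/100: upper limit = 1 - 0.025^(1/100) = 3.6%.
- 1/100: 95% CI 0.0 to 5.4%.
- 5/100: 1.6 to 11.3%; 6/100: 2.2 to 12.6%.

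A patient drops out of a row only if no other post-baseline AE puts that patient there. The any-AE row should therefore move little, and the rare rows (permanent stop, death) relatively more.

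**Step 4: how many patients.** The documents do not say. If a share q of patients has such an AE, the chance that at least one of 100 is omitted is 1 - (1 - q)^100:

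| q (assumed) | expected omitted | chance of at least one |
|---|---|---|
| 0.5% | 0.5 | 39% |
| 1% | 1 | 63% |
| 2% | 2 | 87% |
| 5% | 5 | 99% |

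As a rough anchor, if AE onsets were uniform over 28 days of screening plus 36 months (3 x 365 = 1,095 days), the share starting in screening would be 28/(28 + 1,095) = 2.5%. Only some of those would have a later consequence of the kind in Step 2, which points to the lower rows.

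**The case against.** The strongest reply is that the gap is narrow and partly covered. Protocol 8.1 makes a post-consent worsening of an older condition a new AE; interruptions and study discontinuations are shown without an onset filter; earlier AEs are still listed; patients must be stable on fingolimod and free of medically unstable conditions at entry; and no hypothesis is tested. All of this stands, and it limits the point to the form given here.

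Three stronger readings are tempting, and the documents do not support them.
- A reader might infer that everything arising in the 28 days to 4 months of fingolimod before screening is exposed. The sentence on pre-consent conditions in Protocol 8.1 excludes most of that.
- A reader might infer that every worsening of an open AE is lost because the episode keeps its first date. Protocol 8.1 asks for severity changes to be assessed, and 8.2 ties progression of an SAE to the original report, but neither fixes the start date on the AE page. It is a plausible CRF practice, not a stated rule.
- A reader might suppose that a sizeable share of drug stops would vanish, say 3 of 8. Nothing in the documents supports such a share.

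The objection does not dispose of the core. Listings give no incidence, and permanent drug stops, SAEs and deaths are not counted by incidence elsewhere.

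**Conclusion.** The point holds in limited form. Followed literally, SAP 2.8.1 leaves out of the AE incidence, SOC/PT, severity and death tables any AE that began before Visit 2 and became serious, led to interruption or permanent stop of fingolimod, or was fatal after baseline. For those outcomes this follows directly from the rule. For worsening it depends on how the CRF dates it. The bias is downward. Its size is unknown and probably small: about 1 percentage point per omitted patient at about 100 patients, most noticeable where the count is near zero. The RNFLT analyses are not affected.

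This rests on n of about 100, exact intervals, and the SAP text available. Section 5.2 and part of section 2.1 are not visible there, so an AE rule in those places cannot be excluded. The change should be made because it is cheap and the affected rows are the important ones.

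**What to change.** In SAP 2.8.1, replace selection by onset alone with the following:
- Count types (3), (4), (5) and (7) when the interruption, permanent stop, seriousness or death occurred at or after BL/M0, whatever the AE start date.
- Include those AEs in type (1) and in the SOC/PT tables.
- Also include an earlier AE whose severity worsened at or after BL/M0, where the CRF allows the worsening to be dated. State how a worsening is recorded: as a new AE, or under the existing one.
- Keep all other AEs that began before baseline as listed only.

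The cost is SAP wording and a small derivation. Protocol 6.5 puts the date and reason for stopping drug on the CRF, and Protocol 8.2 provides SAE report and follow-up forms, so the outcome-date part should be derivable. The worsening part is less certain: the AE items listed in Protocol 8.1 include no date of severity change, so check the CRF before committing to it. Reported percentages may rise slightly.

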2.8.1.1 Adverse events of special interest / grouping of AEs

Not applicable

2.8.2 Deaths

See above.

2.8.3 Laboratory data

Abnormal laboratory values or test results constituted adverse events only if they induce clinical signs or symptoms, were considered clinically significant, require medication discontinuation or required therapy. Then they should be documented as AEs. Therefore, no separate analysis of laboratory data applies.

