6.5 Discontinuation of study treatment and premature patient withdrawal

Study drug must be discontinued for a given patient if the investigator determines that continuing it would result in a significant safety risk for that patient. The following circumstances require study drug discontinuation:

- Intolerability of study medication (fingolimod)

- The occurrence of an adverse event or clinically significant abnormality that, in the judgment of the investigator, warrants discontinuation of treatment
- Use of prohibited medications, listed in section 6.4

In addition, the following conditions based on safety monitoring guidelines (See [Appendix 7](#)) should result in fingolimod interruption or discontinuation:

- Ophthalmic:
 - Diagnosis of macular edema
 - Decrease in visual acuity or cystic changes in the macula
- Hepatic:
 - Repeated confirmation of an increase in ALT > 5 x ULN
 - Repeated confirmation of an increase in AST > 5 x ULN
- Blood lymphocyte count less than 100/mm³
- New neurological symptoms accompanied by MRI findings (according to local practice) unexpected for MS

In case of a decrease of visual acuity an immediate ophthalmologic assessment is required. After exclusion of a macula edema or cystic changes in the macula treatment can be continued.

Permanent study drug discontinuation **is required** upon diagnosis of cancerous skin disorders or pregnancy.

Furthermore, all criteria listed under 5.2 for premature patient withdrawal will automatically lead to study drug discontinuation.

In addition to these requirements for study drug discontinuation, the investigator should discontinue study drug for a given patient if, on balance, he thinks that continuation would be detrimental to the patient's well-being.

In addition to scheduled visits, patients who discontinue study drug due to adverse events or abnormalities on safety monitoring tests must be followed up with additional visits as needed in order to confirm the resolution of abnormalities.

Document the date and primary reason for stopping the study drug on the appropriate page of the CRF.

For re-initiation after treatment interruption the same first dose monitoring as for treatment initiation should be repeated if treatment is interrupted for:

- One day or more during the first 2 weeks of treatment
- More than 7 days during weeks 3 and 4 of treatment
- More than 2 weeks after 4 weeks of treatment

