7.6.3 Laboratory evaluation

Routine blood samples (10 ml at each visit; also at unscheduled visits in case of an infection) will be collected at the visits described in [Table 7-1](#) and analyzed by a local laboratory.

Investigators will be asked to comment on any abnormalities on the respective lab result page, including a notation of the clinical significance of each abnormal finding in the patient's source documents. The laboratory sheets will be filed with the patient source documents. Abnormal laboratory values should not be recorded on the adverse event CRF; however, any diagnoses (or signs or symptoms if a diagnosis is not possible) associated with the abnormal findings should be recorded on the adverse event CRF.

Hematology

Hematology parameters will be collected at the visits described in [Table 7-1](#) and [Appendix 2](#) and will include: RBC count, total WBC, differential blood count (lymphocytes), platelet count, hemoglobin, and hematocrit.

Chemistry

Blood samples will be collected at the visits described in [Table 7-1](#) and [Appendix 2](#). Measurements will include the following parameters: sodium, potassium, chloride, calcium, blood urea nitrogen (BUN), random glucose, alkaline phosphatase, creatinine, Bilirubin, ALT, AST, and GGT.

Notable abnormalities are defined in the Criteria for clinically notable laboratory values and vital signs further specified in [Appendix 3](#).

Abnormal laboratory parameters, inconsistent with clinical presentation of MS or suspicious of underlying medical condition, should be repeated for accuracy.

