In case of detection of elevated ALT/AST values > 5 times the upper limit of the normal range (ULN), additional blood chemistry panel including ALT, AST, AP, GGT, total and conjugated bilirubin, albumin should be performed.

If ALT/AST values are repeatedly 5 times the ULN, the study drug must be suspended and not resumed until values have normalized. Patients who develop symptoms suggestive of hepatic dysfunction such as unexplained vomiting or jaundice, should have liver enzymes checked and fingolimod should be discontinued if significant liver injury is confirmed.

In case of isolated elevation of bilirubin over 2.0 mg/dl (34.2 $\mu\text{mol}/\text{L}$), the investigator must discontinue fingolimod administration. Additional evaluations may be performed at the discretion of the investigator.

An interruption or discontinuation of the study drug should be clearly documented and reflected on Dosage Administration Record CRF. AE/SAEs need to be filed as appropriate.

Guidance on monitoring of patients with notable lymphopenia

Fingolimod results in sequestration of a proportion of the circulating lymphocytes in lymph nodes with resultant reduction in circulating lymphocyte counts. Average circulating lymphocytes counts are expected to be around $0.5 - 0.6 \times 10^9 / \text{L}$ or 500- 600 cells/ mm^3 . As such, the absolute total WBC, neutrophil and lymphocyte counts will be measured at each visit by the local laboratory. In case of lymphocyte alert, lymphocyte count should be

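### SAP 2.8.3 omits laboratory analysis because values needing action become AEs, yet under Protocol 7.6.3 a symptom-free value that stops drug can stay off the AE CRF

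*SAP*

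**What the plan says.** SAP 2.8.3 repeats the Protocol 8.1 test for when an abnormal laboratory value is an AE, then draws its conclusion: "Then they should be documented as AEs. Therefore, no separate analysis of laboratory data applies". It does not mention Protocol 7.6.3.

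Protocol 8.1 counts a laboratory value as an AE if it causes signs or symptoms, or if such values "are considered clinically significant, require medication discontinuation or require therapy". It adds: "All adverse events must be recorded on the Adverse Events CRF".

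Protocol 7.6.3 gives a different recording instruction: "Abnormal laboratory values should not be recorded on the adverse event CRF". The same sentence goes on to say that a diagnosis linked to the finding, or a sign or symptom where no diagnosis can be made, does go on that form.

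Protocol Appendix 7 sets laboratory values that act on drug by themselves. For the transaminases: "If ALT/AST values are repeatedly 5 times the ULN, the study drug must be suspended". For bilirubin, the rule begins "In case of isolated elevation of bilirubin over 2.0 mg/dl" and requires the investigator to discontinue. A lymphocyte count confirmed below 100/mm³ also requires discontinuation.

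Protocol 6.5 requires a CRF record whenever drug is stopped: "Document the date and primary reason for stopping the study drug on the appropriate page of the CRF".

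**The concern.** The SAP has one reason for producing no laboratory output: values that matter will already be in the AE data. That holds only if sites follow 8.1. A site that follows 7.6.3 literally, with a patient who has an abnormal value but no symptom and no diagnosis, has nothing to enter on the AE form. The same clinical event is then counted at one site and absent at another.

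Safety and tolerability is a stated secondary objective, and SAP 1.2 makes AE incidence its endpoint. Any error of this kind is an undercount, and no laboratory table or listing exists to show it. Appendix 3 says its notable laboratory criteria cover parameters known to respond to fingolimod, yet SAP section 2.8 plans a shift table of protocol-defined abnormal values for vital signs only.

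**Working it through.** The documents state no figure on this point, so the check is mainly a comparison of texts, followed by one line of arithmetic.

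**Step 1. Which values are AEs, and where they are recorded.** Under 8.1, a value that requires drug discontinuation is an AE and must be on the AE CRF. Under 7.6.3, the value itself must not be; only an accompanying diagnosis, sign or symptom is entered. The two agree when a diagnosis or symptom is entered. They conflict when there is none.

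**Step 2. Whether the protocol creates such cases.** Appendix 7 has three laboratory triggers that need no symptom:

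| Trigger | Required action | Restart rule | AE instruction in that guidance |
|---|---|---|---|
| Repeated ALT/AST at 5 times ULN | Suspend | Yes, once values normalise | File AEs as appropriate |
| Lymphocytes confirmed below 100/mm³ | Discontinue | Yes, above 600/mm³ after discussion with the sponsor | None stated |
| Isolated bilirubin above 2.0 mg/dL | Discontinue | None given | File AEs as appropriate |

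Elsewhere the same appendix is explicit when it wants an AE: newly diagnosed hypertension and all infections are to be reported as AEs.

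**Step 3. Which planned outputs would show the event without an AE record.**
- SAP 2.4.1 displays interruptions with incidence, reason, number and duration. A stop followed by restart should appear there, although it could still be missing from the AE category for temporary interruption.
- SAP 2.3.1 displays reasons for leaving the study. Leaving the study is not the same as stopping drug: Protocol 5.2 does not list a laboratory-triggered stop as a mandatory withdrawal, and 6.5 provides follow-up visits for "patients who discontinue study drug due to adverse events or abnormalities on safety monitoring tests".
- SAP 2.8.1 tabulates AEs that led to permanent discontinuation, but only if an AE was recorded. Its patient listings cover deaths, serious AEs and AEs leading to interruption or dose adjustment, not permanent discontinuation.

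In the SAP text available, the case left uncovered is therefore a permanent stop for a laboratory value, with no diagnosis entered, in a patient who stays in the study. Bilirubin is the clearest example because it has no restart rule.

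**Step 4. Size.** Inputs: N of about 100 (Protocol 10.7, SAP section 3), and m unrecorded patients, which the documents do not give. Maximum loss in incidence = m/N.
- m = 1: 1/100 = 1 percentage point
- m = 3: 3/100 = 3 percentage points
- m = 5: 5/100 = 5 percentage points

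These values of m are illustrative. The loss is a maximum because a patient with another recorded AE still counts under any AE, and one with another AE recorded as the cause of the stop still counts under AE-related discontinuation.

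**The case against.** The strongest defence is that the rules can be read together. Section 8.1 decides what is an AE and says it must be recorded; 7.6.3 is then a convention on wording, under which the site enters a diagnosis rather than a number. Appendix 7 itself uses the term lymphopenia, and its liver guidance reminds sites to file AEs. There are also controls: investigators note the clinical significance of each abnormal result in the source documents (7.6.3), monitors fully verify the recording of data for safety variables (9.1), and key safety data are audited before lock (9.3). Two of the three triggers allow restart and so fall under SAP 2.4.1. All of this stands, and it narrows the problem considerably. It does not remove it: 7.6.3 does not require a diagnosis for a value that stops drug, so capture depends on site practice, and a monitor checking against 7.6.3 as written could accept the missing entry.

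Three stronger readings are tempting but unsupported.
- A reader might infer that laboratory-triggered stops as a class disappear from the report. They do not: a diagnosis entry or SAP 2.4.1 would show many of them.
- A reader might compute that no recorded events in 100 patients gives an exact 95% upper limit of 1 − 0.025^(1/100) = 3.6%, so that four missed patients (4%) would lie outside the reported interval. SAP 2.8.1 prints no laboratory-only rate, and the comparison assumes that every such event is missed at every site.
- A reader might take 6.5, which names adverse events and test abnormalities separately, as a ruling that the latter are not AEs. That sentence concerns who needs follow-up visits, not how events are recorded.

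**Conclusion.** The concern holds in a limited form. The SAP's reason for omitting laboratory analysis relies on 8.1 and overlooks a contrary recording instruction in 7.6.3. A symptom-free laboratory value that stops drug can be absent from the AE incidence tables when the site enters no diagnosis. The main gap is the permanent stop in a patient who remains in the study.

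Each unrecorded patient costs up to 1 percentage point of AE and AE-discontinuation incidence at N of about 100, always towards undercounting. The number of such patients is unknown and may be zero. The primary RNFLT result and the drug-stopping rules are not affected. The conclusion assumes that some sites would follow 7.6.3 literally and that no output outside the SAP text available gives reasons for permanent drug stops. The change is worth making because it is cheap and concerns a stated safety endpoint.

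**What to change.** 1. In SAP 2.8.3, replace the statement that no laboratory analysis applies with one count (n, %, 95% CI) and one listing, in the SAF, of patients whose fingolimod was interrupted or stopped because of a laboratory value. Take these from the reason-for-stopping CRF page (Protocol 6.5) and the Dosage Administration Record (Appendix 7), whether or not an AE was recorded.
2. At the data review meeting already planned before lock, compare these patients with the AE CRF and query any without an AE record. State that 8.1 governs.
3. If sites are still collecting data, add to Protocol 7.6.3, at the next amendment, an exception for values that meet the 8.1 criteria.

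The cost is a small amount of programming, some queries and one amended clause. Because Appendix 1 requires a written amendment for any protocol change, the clause should wait for the next one. No extra patients, visits or blood draws are needed, and laboratory values need not be in the database. The fix assumes that the CRF reason field identifies laboratory reasons. The CRF is not among the documents, so this should be checked first; if the field does not, the review would have to query every drug stop that has no AE record.
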